In this study, we propose implementing health information technology, including automated patient identification and bidirectional secure messaging between clinicians and DSMES providers, and using practice facilitation to address referral barriers and increase clinician awareness and motivation. We have partnered with KDPH (statewide DSMES provider), Kentucky Regional Extension Cooperative (KY-REC, practice facilitation partner), Kentucky Health Information Exchange (health information technology (HIT) partner) and two healthcare systems in rural Kentucky. Our proposal builds on a diabetes quality improvement collaborative facilitated by KY-REC and KDPH that demonstrated increased DSMES utilization. We will use a rigorous study design to evaluate implementation processes and effectiveness by testing the hypothesis that patient identification and referral strategies, bidirectional linkages between clinics and DSMES providers, and primary care clinician engagement will increase DSMES utilization through the following objectives:

Objective 1 – Planning: To use an established implementation science framework (PRISM) to identify determinants of DSMES uptake in Kentucky by interviewing previous DSMES quality improvement collaborative stakeholders, and to adapt the previous intervention using implementation mapping to connect stakeholder determinants to intervention strategies and outcomes.

Objective 2 – Implementation: To implement an intervention comprised of health information technology and a practice facilitation collaborative with two healthcare systems in rural Kentucky to increase DSMES referral rates and gather preliminary data for the planned R01 study.

Objective 3 – Evaluation: To evaluate the pragmatic implementability of the intervention by assessing the feasibility, acceptability, and sustainability of the intervention via stakeholder and participant survey, administrative and interview data.

Study Design

Describe and explain the study design (e.g., observational, secondary analysis, single/double blind, parallel, crossover, deception, etc.).

- **Clinical Research:** Indicate whether subjects will be randomized and whether subjects will receive any placebo.
- **Community-Based Participatory Research:** If you are conducting [community-based participatory research \(CBPR\)](#), describe strategies for involvement of community members in the design and implementation of the study, and dissemination of results from the study.

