Objective 2 is a pragmatic cluster randomized trial. We have partnered with two rural healthcare systems (one in eastern Kentucky and one in Western Kentucky) for this study. Two clinics from each system will be randomized to participate in the intervention (4 total intervention sites) and the remaining clinics will serve as the control sites. The intervention consists of health information technology (including an automated patient identification system and bidirectional e-referral system connecting clinics to the DSMES providers) and a practice facilitation collaborative. The collaborative is a structured, facilitated process that brings together teams from different organizations to learn from one another. The collaborative utilizes the Model for Improvement, a quality improvement approach designed by the Institute for Healthcare Improvement that uses rapid cycle quality improvement – repeated PDSA (plan do study act) cycles meant to identify care quality barriers and rapidly implement and measure change. Teams from intervention clinics will apply this quality improvement strategy to identify and address quality gaps in diabetes care and DSMES utilization at their clinics. Practice facilitators on the study team will provide individualized coaching (practice facilitation) to clinics in the intervention arm of the study. We will assess the effect of the interventions on DSMES referrals (primary outcome), by comparing rates of referrals between intervention and control clinics (clinics within the healthcare system not randomized to the intervention). Secondary outcomes include DSMES attendance, patient satisfaction and diabetes knowledge, A1c control, and intervention feasibility and acceptability.

Objective 3 involves surveys and interviews with clinic staff that participated in the intervention and DSMES providers from the geographic areas where the intervention took place. Interviews will be conducted via phone and audio will be recorded. The goal of Objective 3 is to understand how the various implementation strategies embedded within the practice facilitation collaborative and clinical context influenced DSMES uptake to inform future refinement for program replication and scale-up.

Attachments

Subject Recruitment Methods & Advertising

Describe how the study team will identify and recruit subjects. Please consider the following items and provide additional information as needed so that the IRB can follow each step of the recruitment process.

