Objective 2: Baseline measures include patient demographics (sex, race/ethnicity, insurance coverage, rural/urban distribution), A1c control (mean A1c, % of patients with A1c >9%) and blood pressure. Clinics will also report number of DSMES referrals and DSMES attendance from the 9-month baseline period. In addition to baseline data, control and intervention clinics will generate monthly reports from their electronic health record system to track DSMES referrals and A1c control. DSMES attendance will also be reported by the clinics based on feedback data from the bidirectional referral system linking clinics with DSMES providers. All data will be examined at the clinic level and will be de-identified/aggregated to the clinic level prior to being shared with our study team. The following data is being extracted from patient electronic health records by clinic staff: DSMES referrals (% referred/% eligible at the clinic level), DSMES attendance (% attended/% referred at the clinic level), A1c Data (mean A1c levels and % with A1c >9% at the following time points will be extracted from electronic health record data and de-identified/aggregated into intervention vs control clinics as well as for the subset of patients within intervention vs control clinics that attended DSMES: baseline, monthly during the intervention and for the 6 months following intervention. In addition to the data being extracted from patients' electronic health records, we will also be receiving data from the DSMES providers on patient satisfaction with the class and diabetes knowledge. This outcome will be reported to the study team monthly for all patients from study clinics who attended DSMES classes during the 9-month study + 6 month follow-up period. Patient satisfaction and diabetes knowledge will be evaluated using de-identified data from patient surveys that are routinely collected by DSMES providers for all individuals immediately following DSMES attendance. KDPH will provide the study team with de-identified data for all patients from the two participating healthcare systems who attend DSMES (aggregated to the clinic level). All data used in Objective 2 is data that is routinely collected; no additional data will be collected as a part of the study.

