In this section, please provide the following:

- Describe all sources or methods for obtaining research materials about or from living individuals (such as specimens, records, surveys, interviews, participant observation, etc.), and explain why this information is needed to conduct the study.
- For each source or method described, please list or attach all data to be collected (such as genetic information, interview scripts,

survey tools, data collection forms for existing data, etc.).

- If you will conduct a record or chart review, list the beginning and end dates of the records you will view.

Please see attached file 'Data Collection Summary_UP FOR IT.pdf' for a complete list of data to be collected and surveys/tools for the full list of questions.

Attachments

Attach Type	File Name
DataCollection	PRISM assessment tool.pdf
DataCollection	PRISM Interview Guide.pdf
DataCollection	AIM_IAM_FIM_Implementation Outcomes.pdf
DataCollection	Data Collection Summary_UP FOR IT (Clean).pdf
DataCollection	Data Collection Summary_UP FOR IT (Highlighted).pdf
DataCollection	Interview Guide for Clinic Participants_080922.pdf
DataCollection	Interview Guide for KY REC_080922.pdf
DataCollection	Interview Guide for HLWD_081822_AKD.pdf

Resources

Describe the availability of the resources and adequacy of the facilities that you will use to perform the research. Such resources may include:

- Staffing and personnel, in terms of availability, number, expertise, and experience;
- Computer or other technological resources, mobile or otherwise, required or created during the conduct of the research;
- Psychological, social, or medical services, including equipment needed to protect subjects, medical monitoring, ancillary care, or counseling or social support services that may be required because of research participation;
- Resources for communication with subjects, such as language translation/interpretation services.

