Include a list of services and/or tests that will not be paid for by the sponsor and/or the study (e.g., MRI, HIV). Keep in mind that a subject will not know what is "standard" – and thus not covered by the sponsor/study – unless you tell them.

Objectives 1 and 3: There are no costs associated with participation in the surveys (Objective 3 only) or interviews other than that of the time involved. Providers and other staff will not be given any monetary reimbursement for participating in the study. Their only direct expense associated with the study is that of their time.

Objective 2: The only costs associated with participation in the intervention are that of the time involved and travel costs to the Practice Facilitation Collaboratives.

Data and Safety Monitoring

The IRB requires review and approval of data and safety monitoring plans for greater than minimal risk research or NIH-funded/FDA-regulated clinical investigations.

- If you are conducting greater than minimal risk research, or your clinical investigation is NIH-funded, describe your Data and Safety Monitoring Plan (DSMP). [Click here for additional guidance on developing a Data and Safety Monitoring Plan](#).
- If this is a non-sponsored investigator-initiated protocol considered greater than minimal risk research, and if you are planning on using a Data and Safety Monitoring Board (DSMB) as part of your DSMP, [click here for additional guidance](#) for information to include with your IRB application.

Data and Safety Monitoring Plan

Title: Using Practice Facilitation and Operationalizing Referral Information Technology (UP FOR IT) to Increase DSMES Utilization
 Principal Investigators: [name] PhD and [name] MD MPH

I. Overview

A. The purpose of this study is to pilot test the implementation of health information technology and a practice facilitation collaborative in two healthcare systems in rural Kentucky to increase referrals to and utilization of Diabetes Self-Management Education and Support (DSMES) for patients living with diabetes.

B. The Data and Safety Monitoring Plan (DSMP) outlined below will adhere to the protocol approved by the University of Kentucky IRB.

II. Adverse Events

A. Adverse event assessment

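### Attendance is measured per referral, a denominator the intervention aims to enlarge, so it can fall while utilization rises; name attended/eligible as the between-arm attendance outcome

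*Combined protocol and SAP*

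**What the plan says.** Research Procedures (Objective 2) lists two clinic-level ratios taken from the health record. The first is "DSMES referrals (% referred/% eligible at the clinic level", and the second is "DSMES attendance (% attended/% referred at the clinic level". Referral is the primary outcome. Study Design says its effect will be assessed "by comparing rates of referrals between intervention and control clinics", and adds: "Secondary outcomes include DSMES attendance, patient satisfaction and diabetes knowledge, A1c control, and intervention feasibility and acceptability".

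The stated aim is wider than referral. The hypothesis under Objectives is that "patient identification and referral strategies, bidirectional linkages between clinics and DSMES providers, and primary care clinician engagement will increase DSMES utilization". The overview of the Data and Safety Monitoring Plan gives the purpose as "to increase referrals to and utilization of Diabetes Self-Management Education and Support (DSMES) for patients living with diabetes", which treats referral and utilization as two things. The sample size justification in the same plan says the pilot should indicate roughly how effective the utilization interventions are.

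The intervention acts directly on referral. It includes "an automated patient identification system and bidirectional e-referral system connecting clinics to the DSMES providers".

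No visible section names attended/eligible as an outcome. Data Collection & Research Materials points to an attached summary "for a complete list of data to be collected and surveys/tools for the full list of questions". That attachment was not available and may add a definition.

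**The concern.** The attendance denominator is the numerator of the primary outcome. It is formed after randomisation and is expected to differ by arm if the intervention works. Attended/referred therefore compares differently selected patients in the two arms and is not a randomised comparison of utilization. A clinic that refers many more patients, some less ready to attend, can show a lower attendance percentage while sending more of its eligible patients to class.

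Attendance is the listed secondary outcome closest to utilization, and the pilot is meant to inform a larger study. If attended/referred is the attendance result carried forward, it could point downward, or show nothing, when utilization has improved. Reporting the referral ratio beside it makes the larger denominator visible, but the visible plan does not say the two will be combined.

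**Working it through.** The plan states no attendance rate, effect size or power for this outcome, so there is no figure to reproduce. The check is algebraic, with illustrative rates.

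**Inputs.** The two ratios come from Research Procedures (Objective 2). The 31% referral rate comes from Background, where an outside quality improvement study rose to it from 0%. All other rates are assumptions.

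**Identity.** For one clinic and period, write r = referred/eligible and a = attended/referred, with C for control and T for intervention. If every attendee was referred and the counts match, attended/eligible = r × a.

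**Condition for disagreement.** Attended/referred falls while attended/eligible rises when

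(r_C × a_C) / r_T < a_T < a_C.

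This interval exists whenever r_T > r_C, which is what the primary outcome is meant to show.

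**1. Break-even.** Assume r_C = 10% and a_C = 50%, so attended/eligible in control is 0.10 × 0.50 = 5.0%.

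| r_T | Break-even a_T | Width of disagreement (50% minus break-even) |
|---|---|---|
| 12% | 0.050/0.12 = 41.7% | 8.3 points |
| 15% | 0.050/0.15 = 33.3% | 16.7 points |
| 20% | 0.050/0.20 = 25.0% | 25.0 points |
| 31% | 0.050/0.31 = 16.1% | 33.9 points |

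The zone shrinks towards zero as the referral gain shrinks.

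**2. Range.** Let r_C run over 5–15%, a_C over 40–80% and r_T over 20–31%. The lowest break-even is 0.05 × 0.40 / 0.31 = 6.5%. The highest is 0.15 × 0.80 / 0.20 = 60.0%.

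**3. Case mix alone.** Suppose the 10% who would be referred anyway still attend at 50%, and the added referrals attend at rate q. Then attended/eligible = 0.050 + (r_T − 0.10) × q.

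- r_T = 15%, q = 20%: 0.050 + 0.05 × 0.20 = 6.0% of eligible; 0.060/0.15 = 40.0% of referred.
- r_T = 31%, q = 20%: 0.050 + 0.21 × 0.20 = 9.2% of eligible; 0.092/0.31 = 29.7% of referred.
- r_T = 31%, q = 50%: 0.050 + 0.21 × 0.50 = 15.5% of eligible; 0.155/0.31 = 50.0% of referred.

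In the first two cases the planned measure falls from 50% while utilization rises from 5.0%. In the third there is no reversal, but the planned measure shows no change while utilization goes from 5.0% to 15.5%.

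**The case against.** The strongest reply is that the ratio sits in a list of data to extract and not in an analysis plan. The outcome statements say only that attendance is a secondary outcome, and a between-arm comparison is spelled out only for referrals. The attached data summary may settle the denominator. Both ratios are collected, so a reader can multiply them. Attended/referred is also a sensible measure of referral completion, a step that two-way messaging could improve. Finally, this is a small pilot (four intervention and seven control clinics), and nearly all the rates above are assumed.

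Much of this stands as a limit on the claim. The attachment is unseen, the arm comparison of attendance is inferred from its listing as a secondary outcome, and the numbers show possibility, not likelihood. If two-way linkage raises attendance per referral enough, there is no reversal.

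It does not remove the point. The list gives a specific ratio for attendance, in the same form as the primary outcome, so the visible text does not leave the denominator open. Nothing visible says the two ratios will be multiplied, and the product is valid only under matching conditions that no one has yet been asked to check.

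The replacement has weaknesses of its own. Eligibility is not defined in the visible text and could depend on the identification tool. Unequal capture of attendance would affect either measure.

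**Conclusion.** The concern holds. On the visible text, the attendance outcome has a post-randomisation denominator that the intervention is designed to increase, and no outcome measures the share of eligible patients who attend. Under the assumed control rates the two measures disagree over a zone 8.3 to 33.9 points wide, for intervention referral of 12% to 31%. Across the wider set of assumptions the break-even lies anywhere from 6.5% to 60.0%, so the size in this trial cannot be predicted. The conclusion rests on three things: the unseen attachment does not already define attended/eligible, attendance will be compared between arms, and referral does rise. The change should be made. Confidence is medium because of the first two.

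**What to change.** Name attended/eligible at the clinic level as the between-arm attendance (utilization) outcome, and keep attended/referred as a descriptive step between referral and attendance.

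- Count eligible patients by one rule in both arms, independently of the automated identification tool and over the same period as referrals. The primary outcome needs the same rule because it shares this denominator.
- Compute the outcome from attendee counts. Alternatively, multiply the two planned ratios within each clinic and period, provided the referred counts and periods match and all attendees were referred.
- Confirm that attendance is captured the same way in control clinics. Research Procedures takes clinic-reported attendance from the bidirectional referral system, and the Data Quality and Management section describes validation of reporting for intervention clinics only. The clinic-level data from the state health department could serve as a check if they hold attendee counts.
- Document the change before between-arm results are examined, or label it post hoc.

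The cost is low if both ratios are already held and the matching conditions are met. It is higher if matched counts must be requested retrospectively: the Protocol Changes log shows the field for open enrollment or new data collection set from Y to N in December 2024. The downside is that attendance percentages will look smaller, and the new denominator does not by itself correct unequal capture of eligibility or attendance between arms.

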Objective 2: Data for Objective 2 consists of only data that is routinely collected either via existing surveys (DSMES providers) or electronic health records. All data for this objective will be de-identified (including the full list of HIPAA identifiers) and aggregated to the clinic level prior to being provided to study staff. The study team will not have access to any patient-level identifiable information. The study team will be relying on routinely collected data that is de-identified and aggregated by clinic staff to evaluate outcomes. No identifying information will be used in any report or publication that is produced as part of this study; data will be presented only in the aggregate. Everyone with access to the data will participate in all relevant trainings and will adhere to UKY's high standards for ensuring confidentiality of all data. All study data will be stored in a password protected, cloud-based database only accessible to study team members. Data for Objective #2 will be used to assess the effect of the interventions on DSMES referrals (primary outcome), by comparing rates of referrals between intervention and control clinics (clinics within the healthcare system not randomized to the intervention). Secondary outcomes include DSMES attendance, patient satisfaction and diabetes knowledge, A1c control, and intervention feasibility and acceptability.

Objective #1 and #3: The only information/data gathered on an individual, non-de-identified level are from key informant interviews. All transcriptions and all further thematic analysis and subsequent description for publication or other purposes will be completed without the use of participant names. Any other created paper files will be kept in a locked cabinet and the digital information (e.g., transcripts) will be stored on a secured network. Study files will be maintained for at least five years after final publication of study findings, and then will be shredded/securely discarded.

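### A1c is described as aggregated by arm, against the clinic-level rule for all Objective 2 data, and no N or SD per clinic is named

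*Combined protocol and SAP*

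**What the plan says.** Objective 2 is a pragmatic cluster randomised trial in two rural health systems. Two clinics per system are randomised to the intervention, and the remaining seven of the eleven are controls (Study Design; Data and Safety Monitoring Plan, III.A). DSMES referral is the primary outcome and A1c control is one of several secondary outcomes.

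Research Procedures, Objective 2, sets a general rule: "All data will be examined at the clinic level and will be de-identified/aggregated to the clinic level prior to being shared with our study team". It also says that "control and intervention clinics will generate monthly reports from their electronic health record system to track DSMES referrals and A1c control". Records, Privacy, and Confidentiality repeats the rule for Objective 2: data are "aggregated to the clinic level prior to being provided to study staff".

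The list of extracted items in Research Procedures gives referrals and attendance as percentages by clinic. The A1c item is worded differently. It begins "A1c Data (mean A1c levels and % with A1c >9% at the following time points will be extracted from electronic health record data" and says these are "de-identified/aggregated into intervention vs control clinics as well as for the subset of patients within intervention vs control clinics that attended DSMES".

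The text names no count, denominator or SD to go with the A1c mean or percentage, and it gives no A1c model or error term. The complete variable list is in a Data Collection Summary, cited under Data Collection & Research Materials, which is not part of the available text. Under Objectives, Objective 2 is also meant to "gather preliminary data for the planned R01 study".

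**The concern.** In a cluster randomised trial, the treatment comparison has to be judged against variation between clinics in the same arm. Figures pooled by arm remove that variation. Monthly repeats do not restore it, because each month gives another reading on the same two groups of clinics.

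The choice of rule therefore decides whether A1c can be compared between arms with any valid measure of uncertainty. Staff who follow the specific A1c item would produce something different from staff who follow the general rule, and nothing in the text says which takes precedence.

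A second, smaller matter is what each row contains. If a clinic reports only a mean and a percentage, the variance cannot be split into within-clinic and between-clinic parts. The study team holds only aggregated data, so it could not recover N or SD later by itself. N matters most for the attender subset: the Background puts DSMES use below 10% of people with diagnosed diabetes, so a clinic-month attender mean may rest on very few patients.

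**Working it through.** **1. Design count.** 2 clinics × 2 systems = 4 intervention clinics, and 11 − 4 = 7 controls. This reproduces the figures in the Data and Safety Monitoring Plan, III.A. The text gives no power, SD, ICC or clinic size, so no other figure can be reproduced.

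**2. Degrees of freedom for between-clinic error at one time point** (values received minus parameters fitted):
- A1c by arm: 2 − 2 = 0. There is no error term.
- A1c by clinic: 11 − 2 = 9 (two-sided 5% critical t = 2.262).
- By clinic with health system as a stratum: 11 − 3 = 8 (t = 2.306).
- By clinic with system and the clinic's baseline A1c: 11 − 4 = 7.

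The clinic-level lines need neither N nor SD. For scale, under an assumed 80% power and two-sided 5% level, the noncentral t distribution for 4 versus 7 clinics gives a detectable difference of 1.97 SDs of the clinic means with 9 df, and 2.01 with 8.

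**3. ICC of mean A1c.** ICC = σb² / (σb² + σw²), with σb² = Var(clinic means) − σw²/m, where σw is the within-clinic SD and m the number of patients per clinic. Take an assumed SD of clinic means of 0.3 A1c points (variance 0.09):
- σw = 2.0, m = 50: σb² = 0.09 − 4/50 = 0.01; ICC = 0.01/4.01 = 0.0025.
- σw = 1.5, m = 400: σb² = 0.09 − 2.25/400 = 0.0844; ICC = 0.0844/2.3344 = 0.036.

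The same spread of clinic means fits ICCs about 14 times apart (0.036/0.0025), so N and SD are both needed.

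**4. ICC of the percentage above 9%.** The total variance of a yes/no outcome is p(1 − p), so no SD is needed. Approximately, ICC = [Var(clinic proportions) − p(1 − p)/m] / p(1 − p). With assumed p = 0.15 and an SD of clinic proportions of 0.06:
- m = 50: (0.0036 − 0.00255)/0.1275 = 0.008.
- m = 400: (0.0036 − 0.00032)/0.1275 = 0.026.

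N is therefore needed, and it is enough.

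**5. Precision of an ICC from 11 clinics.** Assume m = 200 and an estimate of 0.02. Then F = 1 + 200 × 0.02/0.98 = 5.08 on 9 and 11 × 199 = 2189 df. Dividing F by the 97.5% and 2.5% points of that F distribution, and converting back with (F − 1)/(F + m − 1), gives a 95% interval of about 0.007 to 0.074.

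All values of p, SD, m and power in steps 2 to 5 are assumptions chosen to show ranges. None is in the documents.

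**The case against.** The best defence is that the A1c item is loose wording and that nobody will pool clinics. The clinic-level rule is stated twice and covers delivery to the study team. Each clinic runs its own monthly report, and the text describes no step in which clinic staff combine A1c across clinics or across the two systems. On this view, the phrase only anticipates a later comparison of arms. That reading is plausible. A reader might infer that A1c will arrive as arm totals, and the documents do not establish that. What remains is the contradiction: the item that deals specifically with A1c gives a different level from the referral and attendance items beside it.

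It is also fair to say that missing N and SD do not destroy the error term. An unweighted comparison of eleven clinic means is valid, and weighting by N is a choice about efficiency. That stands in full. The absence of N and SD bears on the ICC and on reading small subsets.

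Finally, the Data Collection Summary may already list N or SD. That cannot be checked, so the point is limited to what the available text names. The attachment could settle the row contents, but the conflicting sentence would still stand in the protocol.

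**Conclusion.** The point holds as a contradiction to be reconciled. One reading leaves 0 df for between-clinic error in A1c; the other leaves 9, or 8 with health system as a stratum. This result needs only the 4 and 7 clinics given in the documents. On the clinic-level reading the comparison is valid as it stands. In that case the remaining gap is that the ICC of mean A1c cannot be estimated without N and SD, nor that of the percentage without N, unless the unseen attachment supplies them.

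Two stronger inferences are not supported. A reader might conclude that standard errors will be too small because pooled figures are tested as if patients were independent. The documents propose no such test, so no inflation factor applies. A reader might also conclude that the pilot fails a stated aim of supplying an A1c ICC for the R01. The text speaks only of preliminary data. Use of an ICC in planning a later cluster trial is a reasonable inference, and an estimate from 11 clinics would be imprecise in any case.

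A1c is a secondary outcome, and the primary referral outcome is already specified by clinic.

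**What to change.** In Research Procedures, Objective 2, replace the arm-level A1c wording with one row per clinic per month: clinic code, number of patients with an A1c, mean, SD, and count above 9%. Give the same row for DSMES attenders. Bring the Data Collection Summary into line.

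State that A1c is analysed at clinic level, with health system as a stratum and adjustment for the clinic's baseline A1c; weighting by N is optional. Report the between-clinic variance or the ICC with its interval, and note that 11 clinics make it imprecise. If the ICC is meant for the R01, say so.

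The cost is a few extra columns in reports that the clinics already run, with no patient identifiers. The text does not show whether the clinics' record systems can output an SD. The change log shows the application marked as no longer open to enrolment in December 2024, so past reports may have to be re-run. The source is routine record data and the listed end date is 4/1/2026, so this looks feasible. Attender rows with very few patients may need to be accumulated over months to keep the de-identification commitment.
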